### Treatment Duration

For subjects on Avelumab arm, the duration of treatment (weeks) during the study is defined as:

$$\text{Treatment duration (weeks)} = (\text{last dose date} - \text{first dose date} + 14) / 7$$

For subjects on chemotherapy arm (oxaliplatin + 5-FU or oxaliplatin + capecitabine), the duration of treatment (weeks) is defined as follows for both the Induction Phase and the Maintenance Phase, while the first dose and last dose date are relatively to the first and last dose date in the Induction and Maintenance Phase, respectively.

- Oxaliplatin + 5-FU arm:
  - Treatment duration for oxaliplatin (weeks) = (last dose date – first dose date + 14) / 7
  - Treatment duration for 5-FU (weeks) = (last dose date – first dose date + 14) / 7
- Oxaliplatin + capecitabine arm:
  - Treatment duration for oxaliplatin (weeks) = (last dose date – first dose date + 21) / 7Since capecitabine is taken as a tablet twice daily for 2 weeks followed by a 1-week rest period once every 3 weeks, treatment duration is calculated as follows:
  - Treatment duration of capecitabine (weeks) = (last dose date – first dose date + 7) / 7

Duration of Regimen is defined for subjects who receive both oxaliplatin and 5-FU or capecitabine. For these subjects, Duration of Regimen is equivalent to the treatment duration of whichever chemotherapy is discontinued first. For example, if a subject receives oxaliplatin and 5-

---

FU and discontinues oxaliplatin before discontinuing 5-FU, Duration of Regimen will be equal to the treatment duration for oxaliplatin. In the case a subject discontinues oxaliplatin and capecitabine on the same day (and the subject does not receive further capecitabine doses) the treatment duration for oxaliplatin will be selected as the Duration of Regimen for this subject.

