Additionally, subjects receiving avelumab who have experienced a CR should be treated for a minimum of 12 months or until disease progression or unacceptable toxicity, after confirmation of response. In case a subject with a confirmed CR relapses after stopping treatment, but prior to the end of the trial, 1 re-initiation of treatment is allowed at the discretion of the Investigator and after agreement with the Medical Monitor. In order to be eligible for retreatment, the subject must not have experienced any toxicity that led to treatment discontinuation of the initial avelumab therapy. Subjects who re-initiate treatment will stay on trial and will be treated and monitored according to the protocol and follow the Schedule of Assessments until disease progression (see [Table 3](#)).

The treatment should start within 4 days after randomization. While on trial treatment, subjects will be asked to visit the trial site as specified in the Schedule of Assessments (see [Table 3](#), [Table 4](#), [Table 5](#), and [Table 6](#)).

For both avelumab and maintenance chemotherapy, a time window of up to 4 days before or 2 day after the scheduled visit day (-4/ +2 days) will be permitted for all trial procedures. Subjects should return to the target date even if the previous visit was off schedule.

The tumor evaluation (see [Section 7.3](#)) will be performed every 6 weeks (for the first 12 months and every 12 weeks thereafter) with a time window of -5 days for both avelumab and maintenance chemotherapy.

Subjects will receive either:

- Avelumab by IV infusion following pretreatment (see [Section 5.1.2.2.1](#)) once every 2 weeks (see [Section 6.2.1](#)), or
- Maintenance chemotherapy following pretreatment as applicable prior to each infusion (see [Section 6.2.2](#)).

Assessments to be performed during the Maintenance Phase are presented in [Table 3](#) to [Table 6](#).

During the treatment period, the following assessments and procedures will be performed (see [Table 3](#) to [Table 6](#) for the detailed schedule):

- The subject-reported outcomes/QoL assessments will be completed by subjects prior to any trial-related procedures (time points outlined in [Table 3](#) to [Table 6](#)) and then every 6 weeks thereafter.
- AEs and concomitant medications and procedures will be documented at each visit.
- ECOG PS will be assessed at each treatment visit.

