	
For subjects continuing avelumab after initial progressive disease (PD), a radiographic assessment should be performed within 6 weeks of original PD to determine whether there has been a decrease in the tumor size, or continued PD. The assessment of clinical benefit should be balanced by clinical judgment as to whether the subject is clinically deteriorating and unlikely to receive any benefit from continued treatment with avelumab.
 
For subjects receiving avelumab, if discontinuation occurs due to progression and a definitive diagnosis/radiographic confirmation is not made at the time of discontinuation, a second imaging scan may be allowed for confirmation of progression. If progression at the second imaging scan is not confirmed and the subject wishes to restart, the subject will be allowed to continue receiving avelumab as long as they meet the criteria for continuation of treatment beyond progression.
 
If the Investigator feels that the subject continues to achieve clinical benefit by continuing treatment, the subject should remain on the trial and continue to receive monitoring according to the Schedule of Assessments.
 
Any additional continuation of avelumab plus BSC beyond further progression must be discussed and agreed upon with the Medical Monitor. Further disease progression is defined as an additional increase in tumor burden of 20% and <math>\geq 5</math> mm absolute increase in tumor burden from time of initial PD. This includes an increase in the sum of all target lesions and/or the development of new measurable lesions.
 
Subjects receiving avelumab who have experienced a CR should be treated for a minimum of 12 months or until disease progression or unacceptable toxicity, after confirmation of response. In case a subject with a confirmed CR relapses after stopping treatment, but prior to the end of the trial, 1 re-initiation of treatment is allowed at the discretion of the Investigator and after agreement with the Medical Monitor. To be eligible for re-treatment, the subject must not have experienced any toxicity that led to treatment discontinuation of the initial avelumab therapy. Subjects who re-initiate treatment will stay on trial and will be treated and monitored according to the protocol and follow the Schedule of Assessments until disease progression.
 
Subjects in the maintenance chemotherapy arm will receive trial treatment until PD per RECIST v1.1, significant clinical deterioration (clinical progression), unacceptable toxicity, withdrawal of consent, or if any criterion for withdrawal from the trial or trial treatment is fulfilled.

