**Definition of On-Treatment period:**

For the Induction Phase, the on-Treatment period is defined as the time from the first dose of induction chemotherapy treatment through the earliest of (the date of the last dose of Induction chemotherapy + 30 days, start day of new anti-cancer drug therapy – 1 day, date of Maintenance Phase study treatment start – 1 day).

For subjects randomized to the avelumab arm or the control arm and receive chemotherapy, the on-treatment period is defined as the time from the first dose of randomized treatment through the earliest of (last dose of study treatment + 30 days, start day of subsequent anti-cancer drug therapy – 1 day). For subjects randomized to the control arm and receive BSC-only, study treatment is considered to start on the day of the Week 1 Day 1 assessment visit and end on the earliest date given from among the following: date given on the Study Termination eCRF page and date of death. Thus, the on-treatment period for these subjects is defined as the time from the Week 1 Day 1 assessment visit to the earlier of (end of assessment date + 30 days, start of new anti-cancer drug therapy – 1 day).

The date of subsequent anti-cancer drug therapy is derived as outlined in Section 13.2.

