### 11.1 Disposition of Subjects and Discontinuations

Subject disposition summary will be created for the Induction Phase and the Maintenance Phase separately.

For the Induction Phase, the following will be summarized overall and by Induction Phase study treatment for all screened subjects:

- Number of subjects screened
- Number of subjects screen-failed or not treated during Induction Phase
- Number of subjects discontinued during the Induction Phase
- Number and percentage of subjects who completed the Induction Phase treatment
- Primary reasons for treatment discontinuation during the Induction Phase
- Number of subjects completed Induction Phase (overall only)
- Number of subjects completed Induction Phase but not randomized (overall only) and primary reason

Subjects who discontinue Induction Phase chemotherapy due to completion of regimen/randomization to the avelumab or BSC-Only arms will not have the reason presented in the table.

For the Maintenance Phase, the following will be summarized overall and by treatment arm (as randomized) for all randomized subjects:

- Number of subjects randomized
- Number and percentage of subjects randomized but not treated (among those randomized to chemotherapy or avelumab)
- Number and percentage of subjects randomized to the control arm who received BSC-Only
- Number and percentage of randomized subjects still on study treatment
- Number and percentage of randomized subjects who discontinued all study drugs
- Number and percentage of subjects who discontinued any one study treatment and primary reason by study drug, i.e. avelumab, oxaliplatin, 5-FU, capecitabine.
- Number and percentage of subjects who discontinued treatment but are still in follow-up

- Number and percentage of subjects who discontinued the study and primary reasons
- Number and percentage of subjects who re-initiated avelumab treatment
- Number and percentage of subjects who discontinued avelumab treatment after re-initiation and primary reasons
- Number and percentage of subjects in the following analysis sets:
  - Safety-Induction
  - FAS
  - PP
  - Safety-Maintenance
  - HRQoL
  - PD-L1+
- The number of subjects randomized by region and country
- Cross tabulation: subjects randomized (avelumab, oxaliplatin + 5-FU, oxaliplatin + capecitabine, or BSC-Only, Total) versus subjects treated (avelumab, oxaliplatin + 5-FU, oxaliplatin + capecitabine, BSC-Only, or Not Treated).

In addition, the following will be summarized:

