### **Cumulative Dose**

The overall cumulative dose (mg/kg) of avelumab per subject across all cycles is the sum of the actual dose levels that the subject received (i.e. total dose administered (mg) / weight (kg)).

The overall cumulative dose (mg/m^2) of oxaliplatin, 5-FU, and capecitabine per subject across all cycles is the sum of the actual dose levels that the subject received (i.e. total dose administered (mg) / BSA (m^2)).

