### **Dose Intensity**

The dose intensity (DI) will be calculated for each subject across all cycles. Each cycle is defined by a 2-week period for avelumab and oxaliplatin + 5-FU and by a 3-week period for Oxaliplatin + Capecitabine.

The dose intensity of avelumab (mg/kg/cycle), oxaliplatin (mg/m^2/cycle), 5-FU (mg/m^2/cycle), and capecitabine (mg/m^2/cycle) is defined as

$$DI = \left( \frac{\text{cumulative dose}}{\frac{\text{duration of therapy (in weeks)}}{\text{number of weeks per cycle}}} \right)$$

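### For avelumab subjects re-treated after a CR relapse, the off-drug gap counts as treatment duration and holds the on-treatment window open, so dose intensity is understated and unexposed time enters the safety period

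*SAP*

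**What the plan says.** **Re-treatment is foreseen.** After a confirmed complete response that relapses off treatment, Protocol 7.1.4 states that "1 re-initiation of treatment is allowed at the discretion of the Investigator and after agreement with the Medical Monitor". SAP 5 repeats the rule and adds: "Subjects who re-initiate treatment will stay on trial and will be treated and monitored according to the protocol". On the first course, SAP 5 says: "Subjects receiving avelumab who have experienced a CR should be treated for a minimum of 12 months", counted from confirmation of the response, unless progression or toxicity ends it sooner. SAP 11.1 plans to report "Number and percentage of subjects who re-initiated avelumab treatment" and the discontinuations that follow re-initiation. In the readable text, re-initiation enters no other analysis rule.

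**Exposure.** SAP 14 reads "For subjects on Avelumab arm, the duration of treatment (weeks) during the study is defined as" (last dose date − first dose date + 14)/7. On the dose side, "The overall cumulative dose (mg/kg) of avelumab per subject across all cycles is the sum of the actual dose levels that the subject received". Then "The dose intensity (DI) will be calculated for each subject across all cycles", as cumulative dose divided by the number of two-week cycles in that duration. RDI is this value over the planned dose per cycle, reported in bands of which the lowest is below 80%. The dose-delay rule in the same section measures each infusion against the previous one. Its top category is 7 days or more, and the longest delay per subject is tabulated.

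**On-treatment window.** SAP 10 defines it for active treatment as "the time from the first dose of randomized treatment through the earliest of (last dose of study treatment + 30 days" or the day before a new anti-cancer drug starts). Protocol 8.5.1 has the same single window, unless otherwise stated. Treatment-emergent adverse events (SAP 16.1), the safety tables (SAP 16) and concomitant medications (SAP 13.1) all depend on it.

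**The concern.** The dose sum has nothing in it for the weeks off drug, but the duration it is divided by contains all of them. A subject who received every scheduled dose in both courses can therefore be reported in the lowest RDI band, and the first re-treatment dose would be classed as a delay of 7 days or more.

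The window has the same fault. Its 30-day tail means that time more than 30 days after dosing should not count as on-treatment. For a re-treated subject, the rule counts that time anyway, up to the restart. The opposite failure is also possible. If a new anti-cancer drug is started during the gap, the window closes the day before it and never reopens, so events on the re-treatment course are not treatment-emergent.

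Re-initiation is written for avelumab only, and Protocol 6.2.2 stops maintenance chemotherapy at the first radiological progression. The distortion therefore falls on one arm.

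**Working it through.** The documents state no exposure result to reproduce, so the SAP formulas are applied directly.

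**Inputs from the documents:** 10 mg/kg every 2 weeks; duration = (last − first + 14)/7 weeks; dose intensity = cumulative dose/(duration/2); RDI = dose intensity/10; window = first dose to last dose + 30 days, counted inclusively.

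**Assumptions (not in the documents):** 26 first-course doses; a gap of g weeks beyond the normal 2-week interval, with g from 8 to 52; 3, 6 or 13 re-treatment doses; every dose given in full; no new anti-cancer drug.

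**Check without a gap.** 26 doses fall on days 0 to 350. Duration = (350 + 14)/7 = 52 weeks, dose intensity = 260/26 = 10 mg/kg per cycle, RDI = 100%. The formula works for one unbroken course.

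**Case with g = 26 and 6 re-treatment doses**
- Second course starts on day 350 + 14 + 182 = 546 and ends on day 546 + 70 = 616.
- As written: duration = (616 + 14)/7 = 90 weeks; dose intensity = 320/45 = 7.11; RDI = 71.1%.
- Summed by course: 52 + 12 = 64 weeks; dose intensity = 320/32 = 10; RDI = 100%.
- Window as written: 616 + 31 = 647 days. By course: (350 + 31) + (70 + 31) = 482 days. Excess: 165 days.
- Delay rule: the next infusion after day 350 was due on day 364, so the dose on day 546 is 182 days late.

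**General form.** With T = 2 × (number of doses), RDI = T/(T + g). The excess window is (14 + 7g) − 31 = 7g − 17 days. For 26 + 6 doses, T = 64:

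| Gap (weeks) | RDI as written | Excess on-treatment days |
|---|---|---|
| 8 | 64/72 = 88.9% | 39 |
| 12 | 64/76 = 84.2% | 67 |
| 16 | 64/80 = 80.0% | 95 |
| 26 | 64/90 = 71.1% | 165 |
| 52 | 64/116 = 55.2% | 347 |

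Across all the assumed combinations, RDI runs from 58/110 = 52.7% (3 doses, 52 weeks) to 78/86 = 90.7% (13 doses, 8 weeks). It falls below 80% once g exceeds T/0.8 − T, which is 14.5, 16.0 or 19.5 weeks for 3, 6 or 13 re-treatment doses.

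**Longer first course.** The 12 months run from confirmation of response. A response first seen at the 6-week scan and confirmed 4 weeks later gives 6 + 4 + 52 = 62 weeks, or 31 doses. With g = 26 and 6 re-treatment doses, RDI = 74/(74 + 26) = 74%, so the effect is slightly smaller.

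**What is collected in the 165 excess days.** Protocol 7.1.6 and 7.1.7 collect all adverse events to the 30-day visit, serious and treatment-related non-serious events to day 90, and after that newly report only serious events judged related. The first 60 excess days (days 381 to 440) have partial collection. The remaining 105 (days 441 to 545) have related serious events only.

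**The case against.** The case for leaving the text alone has several sound parts.

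- **Few subjects.** A subject must have a confirmed complete response, stop, relapse off drug, meet the re-treatment condition and restart before the data cut-off. The documents give no count. With 499 randomized 1:1, an arm has about 250 subjects, so each one moves an RDI band by about 1/250 = 0.4 percentage points.
- **Adverse event tables.** A reader might infer that every off-drug event and laboratory value in the gap is charged to avelumab. The documents do not support this. Collection narrows at 30 and again at 90 days, the avelumab assessment schedule (Protocol Table 6) has no safety laboratory tests in long-term follow-up, and late newly reported events are ones already judged related. SAP 16.1 reports percentages of subjects, and no person-time rate is visible, so the extra days change a table only if a recorded event falls in them.
- **Other restarts.** A reader might extend the point to restarts after unconfirmed progression. Those are pauses pending a second scan, in effect missed doses within one course, and RDI is meant to show them.
- **Transparency.** Exposure and dosing listings by subject, together with the re-initiation counts, would let a careful reader find the affected subjects.

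These arguments limit the size and the scope. They do not make the formula right for a re-treated subject, and a listing does not correct a summary table. Incomplete collection is itself a reason not to call the gap on-treatment.

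**Conclusion.** The definitions give a wrong result, as written, for subjects re-initiated after a CR relapse. Duration is overstated by the length of the gap and dose intensity and RDI are understated to match. The first re-treatment dose is misclassed as a delay. The on-treatment window either runs through unexposed, partly observed time or, if a new anti-cancer drug intervenes, leaves out the re-treatment course. Cumulative dose is correct.

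The effect can be large for one subject but is probably small for the arm. The figures rest on the assumed doses and gaps, because the documents give neither. This is a point about exposure and safety summaries. It should not be read as a threat to the efficacy conclusions: overall survival, alpha and power do not use these definitions.

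**What to change.** For re-initiation after a CR relapse only, amend SAP 10 and 14 as follows:

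1. Define first and last dose for each treatment course.
2. Take duration as the sum of (last − first + 14)/7 over courses, and base dose intensity and RDI on that sum.
3. Define on-treatment as the union of each course's first dose to last dose + 30 days, with each course ended early only by a new anti-cancer drug started during or after that course.
4. Do not count the gap between courses as a dose delay.
5. State that short pauses pending a second scan after unconfirmed progression stay within one course.
6. List the departure from the Protocol 8.5.1 window in SAP 8, which now declares one exception.

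The cost is SAP wording and a small change to the derivations, using dosing dates already collected. Protocol 8.5.1 requires a protocol amendment only if the sponsor regards the change as major. No clinical rule changes.

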7.1.2 Induction Phase Treatment Period

In this trial, the treatment will be given until PD, significant clinical deterioration (clinical progression), unacceptable toxicity, or any criterion for withdrawal from the trial or trial treatment is fulfilled (see Section 5.5.1).

Treatment during the Induction Phase will consist of:

- 6 cycles of oxaliplatin (85 mg/m² IV on Day 1 every 2 weeks) + leucovorin (200 mg/m² IV on Day 1 every 2 weeks or equivalent levoleucovorin dose) followed by 5-FU (2600 mg/m² IV continuous infusion over 24 hours on Day 1 every 2 weeks,

OR

Oxaliplatin at 85 mg/m² IV on Day 1 with leucovorin 400 mg/m² IV on Day 1 (or equivalent levoleucovorin dose) followed by 5-FU at 400 mg/m² IV push on Day 1 and 2400 mg/m² IV continuous infusion over 46-48 hours (Days 1 and 2) given every 2 weeks (for up to 12 weeks).

OR

- 4 cycles of Oxaliplatin (130 mg/m² IV on Day 1 every 3 weeks) + Capecitabine (1000 mg/m² PO twice daily on Days 1-14). Capecitabine tablets should be swallowed with water within 30 minutes after a meal.

All the laboratory samples and vital signs will be collected prior to each drug administration. Administration of chemotherapy will take place only after relevant results have been checked by a medically qualified person and criteria for dosing have been met.

During the treatment period, the following assessments and procedures will be performed (see [Table 1](#) and [Table 2](#) for the detailed schedule):

- SAEs, AEs and concomitant medications and procedures will be documented at each trial visit.
- ECOG PS will be assessed at Day 1 of each treatment cycle (Screening ECOG PS may be used for Cycle 1 Day 1 if it was performed within 3 days prior to Day 1).
- Physical examinations will be performed on Day 1 of each treatment cycle. Such examinations will include a comprehensive skin examination for tumor.
- Vital signs and body weight will be assessed at each visit.
- Body weight will be assessed at Day 1 of each cycle.
- The laboratory hematology and hemostaseology, will be assessed on Day 1 of each cycle. Core serum chemistry tests will be assessed at Day 1 of each cycle. A full urinalysis will be performed at Screening and the End-of-treatment visit. Subjects should also return to the site as per local institutional practice for any additional routine assessments during chemotherapy.

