**Definition of duration:**

Duration will be calculated by the difference of start and stop date + 1, if not otherwise specified. For example, survival time (days) = date of death – date of randomization + 1.

The time since an event (e.g. time since first diagnosis) will be calculated as reference date minus date of event.

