## 14 Treatment Compliance and Exposure

*Analysis sets: Safety-Induction Analysis Set, Safety-Maintenance Analysis Set*

All dosing calculations and summaries will be based on the administration of study medications from the corresponding eCRF pages.

All subjects enrolled in this trial will start with a 12-week chemotherapy Induction Phase during which subjects receive oxaliplatin and either 5-FU or capecitabine (according to the dosing schedule in Section 6.2.2 and Table 2 in the CTP).

Subjects who experience a CR, PR, SD, or Non-CR/ Non-PD at the end of Induction Phase will be randomized to the Maintenance Phase.

**Best Supportive Care (BSC):** Best supportive care is defined as: treatment administered with the intent to maximize quality of life without a specific antineoplastic regimen.

Maintenance Phase treatment arms are as follows:

- **Avelumab arm:** Subjects randomized to the avelumab arm will receive an IV infusion of avelumab at a dose of 10 mg/kg (over the duration of 1 hour) once every 2 weeks (one cycle).
- **Chemotherapy/BSC arm:** Following the completion of the Induction Phase, site investigators will determine whether subjects are eligible to receive further chemotherapy during the Maintenance Phase. Subjects randomized to the Chemotherapy/BSC-only arm will receive the following:
  - **Oxaliplatin + 5-FU:** If subjects are deemed eligible to receive further chemotherapy and received oxaliplatin + 5-FU in the Induction Phase, they will receive the same regimen as they received in the Induction Phase, e.g. Oxaliplatin at 85 mg/m^2 IV on Day 1 plus leucovorin 200 mg/m^2 IV on Day 1 followed by 5-FU at 2600 mg/m^2 IV continuous infusion over 24 hours on Day 1, once every 2 weeks. Please refer to the CTP for alternative dosage/administration schedules.

- **Oxaliplatin + Capecitabine arm:** If subjects are deemed eligible to receive further chemotherapy and received oxaliplatin + capecitabine in the Induction Phase, they will receive the same regimen as they received in the Induction Phase, i.e. oxaliplatin at 130 mg/ m^2 IV on Day 1 with capecitabine at 1000 mg/m^2, twice daily for 2 weeks followed by a 1-week rest period once every 3 weeks.
- **BSC-Only:** Subjects who are not deemed eligible to receive further chemotherapy will receive BSC alone with no active therapy.

Analysis of exposure will be based on the calculated actual dose levels:

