### **Relative Dose Intensity**

The relative dose intensity (RDI) is defined as the actual dose intensity divided by the planned dose per cycle and expressed in %.

The summary of treatment exposure and compliance will be calculated for both Induction Phase and Maintenance Phase, and will include the following information:

- Duration of therapy (weeks)
- Total number of infusions received (avelumab and IV chemotherapy)
- Total number of Capecitabine doses received

The following will be included, broken down by separate chemotherapy treatment in the chemotherapy arm:

- Cumulative dose of therapy (mg/kg or mg/m^2)
  - Dose intensity (mg/kg/cycle) or (mg/m^2/cycle)
-

- Relative dose intensity of therapy categories: < 80%, 80% - < 90%, 90% - < 110%, >= 110%

A listing of treatment exposure and compliance will also be created to summarize the information listed above for each subject.

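### With capecitabine on Days 1 to 14, the SAP's duration formula is one day short, so capecitabine dose intensity is slightly overstated

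*SAP*

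**What the plan says.** SAP section 14, Treatment Duration, gives a separate formula for each drug, to be used in both the Induction and the Maintenance Phase. For capecitabine it is "Treatment duration of capecitabine (weeks) = (last dose date – first dose date + 7) / 7". The sentence before it explains the choice by the schedule of two weeks on tablets and one week off. For oxaliplatin in the same arm, 21 days are added to the difference between last and first dose dates.

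Protocol section 7.1.2 gives capecitabine "PO twice daily on Days 1-14". SAP section 14 describes the Maintenance regimen as "twice daily for 2 weeks followed by a 1-week rest period once every 3 weeks", without numbering the days.

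Dose intensity is cumulative dose divided by the number of cycles, where the number of cycles is duration in weeks divided by weeks per cycle. The cycle is defined "by a 3-week period for Oxaliplatin + Capecitabine". For the relative measure, the SAP says: "The relative dose intensity (RDI) is defined as the actual dose intensity divided by the planned dose per cycle and expressed in" per cent. It is reported in bands: "Relative dose intensity of therapy categories: < 80%, 80% - < 90%, 90% - < 110%, >= 110"%.

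SAP section 10 also sets a default: "Duration will be calculated by the difference of start and stop date + 1, if not otherwise specified".

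**The concern.** The 7 days in the capecitabine formula are evidently the rest week. A span counted from first to last dosing day inclusive also needs one more day, as in the SAP's default rule, and that day is missing. The capecitabine formula is specified separately, so the default does not bind it, but the SAP gives no reason for leaving the day out.

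Two things follow. Capecitabine and oxaliplatin, given to one subject over the same cycles, receive different durations. A subject who takes every planned tablet also scores above 100% on relative dose intensity. At stake is the accuracy of a descriptive exposure table: capecitabine duration, dose intensity and relative dose intensity in both phases, and Duration of Regimen where capecitabine is the drug stopped first.

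**Working it through.** **Inputs**

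- Dosing days 1 to 14 (protocol 7.1.2).
- 1000 mg/m² twice daily (protocol 7.1.2 and Table 9), so the planned dose per cycle is 1000 × 2 × 14 = 28,000 mg/m².
- Cycle of 3 weeks, or 21 days (SAP section 14, Dose Intensity).
- Days added after last minus first dose date: 7 for capecitabine, 21 for oxaliplatin (SAP section 14, Treatment Duration).

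**Target.** A subject who completes k cycles on schedule should have a duration of 21k days.

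**Oxaliplatin, same arm.** The dose falls on Day 1, so last minus first is 21(k − 1). Adding 21 gives 21k. For the four-cycle Induction: 63 + 21 = 84 days, which is 12 weeks.

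**Capecitabine.** Last minus first is 21(k − 1) + 13. Adding 7 gives 21k − 1. For one cycle: 13 + 7 = 20 days. For four cycles: 76 + 7 = 83 days.

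**Dose intensity after one full cycle.** 20 days is 2.857 weeks. Dose intensity = 28,000 / (2.857 / 3) = 29,400 mg/m² per cycle. Relative dose intensity = 29,400 / 28,000 = 105.0%.

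In general, with full dosing, relative dose intensity is 21k / (21k − 1):

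| Cycles | Formula (days) | Schedule (days) | Relative dose intensity |
|---|---|---|---|
| 1 | 20 | 21 | 105.0% |
| 2 | 41 | 42 | 102.4% |
| 4 | 83 | 84 | 101.2% |
| 6 | 125 | 126 | 100.8% |

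**Effect on the bands.** Divide each cut-off by the same factor, again with the last dose on Day 14.

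- One cycle (factor 1.050): 90 / 1.050 = 85.7 and 80 / 1.050 = 76.2. A true value from 85.7% to below 90% is reported as 90% or more, and one from 76.2% to below 80% as 80% or more.
- Four cycles (factor 1.012): 90 / 1.012 = 88.9. Only a true value from 88.9% to below 90% crosses the 90% cut-off.
- A fully dosed subject, at most 105.0%, stays in the 90% to below 110% band.

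**Check with +8.** Last minus first plus 8 gives 21(k − 1) + 21 = 21k, so relative dose intensity is 100.0% for any number of full cycles.

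**Sensitivity to the last dosing day (one cycle, all 28 doses taken).**

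| Last dose dated | With +7 | With +8 |
|---|---|---|
| Day 14 | 20 days, 105.0% | 21 days, 100.0% |
| Day 15 | 21 days, 100.0% | 22 days, 95.5% |
| Day 16 | 22 days, 95.5% | 23 days, 91.3% |

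**The case against.** A reader might infer that capecitabine dose intensity is overstated in every subject. The documents do not support that. Days 1 to 14 are written out only in the Induction text; protocol Table 9 and SAP section 14 say two weeks on and one week off and fix no time for the first dose. If the 28 doses run from the evening of Day 1 to the morning of Day 15, which the documents neither state nor exclude, the present formula gives exactly 21 days. If the last dose is later still, relative dose intensity falls below 100%. The eCRF pages that hold the dose dates are not part of the documents, so how the last dose date is recorded cannot be checked. This part of the objection stands and limits the finding to Day 14 endings. Those are the only numbered dosing days that the documents give.

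A reader might also infer that control-arm exposure as a whole is biased upwards. It is not. Duration is biased downwards by one day, cumulative dose does not use duration, and the oxaliplatin and 5-FU figures do not depend on this formula. When oxaliplatin and capecitabine stop on the same day, Duration of Regimen takes the oxaliplatin value.

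Nor is a shortfall in tablets hidden altogether. The SAP's Dose Reductions rule flags any Maintenance cycle with a non-zero dose below 90% of plan and counts skipped capecitabine doses as planned. It does not use duration, so a one-cycle Maintenance subject at a true 86% to 89% would still be flagged. Induction has no such check.

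Comparison with the 5-FU formula would be weaker evidence, because one 5-FU regimen runs into Day 2. The comparison with oxaliplatin is enough.

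**Conclusion.** The formula is wrong as written for the only dosing days that the protocol numbers. Capecitabine duration is one day short in total, whatever the number of cycles. Relative dose intensity is therefore overstated by 5.0% at one cycle, but by only 1.2% at the four cycles of a completed Induction and by less than 1% from six cycles on. Only a subject near a cut-off changes band.

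This rests on the last dose of a cycle being dated Day 14. The effect is confined to descriptive exposure summaries. No analysis of survival, progression or response uses the formula, and type I error is not touched. It is a minor correction, worth making because it is nearly free and because the two drugs of one regimen should not show different durations over the same completed cycles.

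**What to change.** In SAP section 14, Treatment Duration, change the capecitabine formula to (last dose date − first dose date + 8) / 7 for dosing on Days 1 to 14.

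State the dosing-day convention next to it, namely which calendar day counts as the last dosing day of a cycle. Without that statement +8 is not safe: a last dose dated Day 15 would give 22 days and a relative dose intensity of 95.5% after one full cycle, an error in the other direction.

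The cost is one digit and one sentence in the SAP, one digit in the exposure program, and a rerun of the capecitabine exposure tables and listing. No new data are needed.
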